- Clinical Laboratory Inclusion Criteria: The following laboratory results must be met within 14 days (or as stipulated) prior to study drug (treatment) administration:
 - a. Absolute neutrophil count (ANC) ≥ 1000 cells/µl (growth factor cannot be used within the previous 7 days).
 - Aspartate aminotransferase (AST) and alanine aminotransferase (ALT) ≤ 2.5 × upper limit of normal (ULN).
 - Platelet count ≥ 50,000/µl (without platelet transfusion in the previous 7 days).
 - d. Total bilirubin ≤ 1.5 mg/dL.
 - e. Serum creatinine ≤ 2.0 mL/dL and creatinine clearance ≥ 40 mL/min (calculated by the Cockcroft-Gault Equation or per 24 hour urine collection).

- Serum albumin ≥ 3.2 g/dL.
- g. Serum creatine phosphokinase (CPK) $\leq 2.5 \times$ the ULN.
- Serum calcium (corrected for albumin) level at or below the ULN range (treatment of hypercalcemia is allowed and subject may enroll if hypercalcemia returns to normal range with standard treatment).
- Left ventricular ejection fraction (LVEF) ≥ institutional lower limit of normal as measured by
 multigated acquisition scan (MUGA) scan or 2-dimensional echocardiography (ECHO) within 28 days
 prior to start of therapy and no clinically significant abnormalities on a 12-lead electrocardiogram
 (ECG).
- 9. Females of childbearing potential (FCBP)* must have a negative serum or urine pregnancy test prior to initiation of the SL-401 Run in Cycle (if required) and repeated with a sensitivity of at least 50 mIU/mL within 10 − 14 days prior to and again within 24 hours of starting POM and must either commit to continued abstinence from heterosexual intercourse or begin 2 acceptable methods of birth control, 1 highly effective method and 1 additional effective method at the same time, at least 28 days before she starts taking POM through 30 days after the last dose of POM and 60 days after the last dose of SL-401. FCBP must also agree to ongoing pregnancy testing during the entire duration of treatment. Men must agree to use a latex or synthetic condom during sexual contact with a FCBP even if they have had a vasectomy from the time of signing the informed consent form through 60 days after the last dose of POM or SL-401. These same patients must not donate sperm. All patients must be counseled at a minimum of every 28 days about pregnancy precautions and risks of fetal exposure. All patients enrolled into this study, must agree to be registered in and must comply with all requirements of the POM REMS™ program.

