Dose Level		SL-401 (IV) Daily on Days 1 – 5	POM (oral) Daily on Days 1 – 21	DEX (oral) on Days 1, 8, 15 and 22
-1	5 μg/kg	5 μg/kg	4 mg	40 mg
1	7 μg/kg	7 μg/kg	4 mg	40 mg
2	9 μg/kg	9 μg/kg	4 mg	40 mg
3	12 μg/kg	12 μg/kg	4 mg	40 mg

Cohorts of 3-6 patients will be treated at each dose level. All patients within a cohort must complete the Run-in Cycle and the first cycle of combination therapy (Cycle 1) before patients can be enrolled into the subsequent cohort of SL-401 (single agent) at the next higher dose. No intra-patient dose escalation is allowed. The first cohort of patients will receive SL-401 single agent at a dose of 7 µg/kg/day followed by SL-401 with POM/DEX. After all patients in this cohort complete the Run-in Cycle and Cycle 1 of combination therapy, the dose for the second cohort of patients will increase to 9 µg/kg/day, conditional on the dose-limiting toxicity (DLT) rules described below. Similarly, after all patients in the second cohort complete the Run-in Cycle and Cycle 1 of therapy, the dose for the third cohort of patients will increase to 12 µg/kg/day, conditional on the dose-limiting toxicity (DLT) rules described below.

DLT Assessment:

Run-in Cycle:

In order to be evaluable for DLT assessment during the single agent Run-in Cycle, all patients must complete 5 doses of therapy (5 doses over a period not to exceed 10 days in the setting of specific AEs) and complete the 28 days of observation unless the patient experiences DLT (patients who discontinue prior to this juncture because of disease progression or for reasons unrelated to study therapy will be replaced).

Combination Therapy:

In order to be evaluable for DLT assessment of the combination therapy, a patient must receive at least 3 infusions of SL-401 and 16 (approximately 75%) doses of POM during Cycle 1, and complete the 28 days of observation unless the patient experiences DLT (patients who discontinue prior to this juncture because of disease progression or for reasons unrelated to study therapy will be replaced).

During phase 1, DLT is defined as any of the following AEs that are possibly, probably or definitely related to therapy:

- Any grade ≥ 4 neutropenia lasting greater than 7 days or grade ≥ 3 neutropenia associated with fever.
- Any grade ≥ 4 thrombocytopenia lasting greater than 7 days or grade ≥ 3 thrombocytopenia associated with bleeding.
- Any grade ≥ 3 non-hematologic toxicity except:

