6.2.1 Phase 1: Dose Escalation

Run-In Cycle: SL-401 will be evaluated at doses of 7, 9, or 12 μg/kg/day, for 5 consecutive days (Days 1-5; with postponement as required by adverse events such that 5 doses over 10 days is permitted) as single agent during an initial Run-in Cycle. Upon completion of the Run-in Cycle patients will be evaluated for safety and response.

- Patients who do not experience a DLT during the Run-in Cycle will have POM/DEX added to their regimen at the assigned cohort dose.
- Patients who experience a DLT during the Run-in Cycle will be discontinued from study.

Table 7 details the SL-401/POM/DEX dose levels, beginning with dose level 1 to be evaluated.

Table 7: Dose Levels to be Evaluated

Dose Level	DLT EVALUTION PERIOD = RUN IN CYCLE and CYCLE 1				
	Run-In Cycle	Combination therapy Cycles 1 - 6			
	SL-401(IV) Daily on Days 1 – 5	SL-401(IV) Daily on Days 1 – 5	POM (oral) Daily on Days 1 – 21	DEX (oral) on Days 1, 8, 15 and 22	
-1	5 μg/kg	5 μg/kg	4 mg	40 mg	
1	7 μg/kg	7 μg/kg	4 mg	40 mg	
2	9 μg/kg	9 μg/kg	4 mg	40 mg	
3	12 μg/kg	12 μg/kg	4 mg	40 mg	

Cohorts of 3-6 patients will be treated at each dose level. All patients within a cohort must complete the Run-in Cycle and the first cycle of combination therapy (Cycle 1) before patients can be enrolled into the subsequent cohort of SL-401 (single agent) at the next higher dose. No intra-patient dose escalation is allowed. The first cohort of patients will receive SL-401 single agent at a dose of 7 µg/kg/day followed by SL-401 with POM/DEX. After all patients in this cohort complete the Cycle 1 of therapy, the dose for the second cohort of patients will increase to 9 µg/kg/day, conditional on the DLT rules described below. Similarly, after all patients in the second cohort complete Cycle 1 of therapy, the dose for the third cohort of patients will increase to 12 µg/kg/day, conditional on the DLT rules described below.

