6.2.2 Dose limiting Toxicity Definition

Run-In Cycle

In order to be evaluable for DLT assessment during the Run-in Cycle of single agent SL-401, a patient must receive all 5 doses within a 10 day time period (Days 1 – 10) and complete the 28 days of observation unless they experience DLT (patients who discontinue prior to this juncture because of disease progression or for reasons unrelated to study therapy will be replaced).

Combination Therapy Initial Cycle (Cycle 1)

In order to be evaluable for DLT assessment in Cycle 1 (initial cycle of combination therapy), a patient must receive at least 3 infusions of SL-401 and 16 (approximately 75%) doses of POM during Cycle 1, and complete the 28 days of observation unless they experience DLT. (Patients who discontinue prior to this juncture because of disease progression or for reasons unrelated to study therapy will be replaced).

The period of evaluation for DLT will include Run-in Cycle and Cycle 1 (the initial cycle of combination therapy).

DLT is defined as any of the following treatment-emergent adverse events (TEAEs) that are possibly, probably, or definitely related to therapy occurring in the first cycle:

- Any ≥ grade 4 neutropenia lasting greater than 7 days or ≥ grade 3 neutropenia associated with fever.
- Any grade ≥ 4 thrombocytopenia lasting greater than 7 days or ≥ grade 3 thrombocytopenia associated with bleeding.
- Any ≥ grade 3 non-hematologic toxicity except:
 - Grade 3 nausea, vomiting, or diarrhea lasting no longer than 48 hours (with resolution to ≤ grade 1 or baseline) with optimal supportive care.
 - Grade 3 arthralgia, myalgia, fever, in the absence of neutropenia, lasting no longer than 48 hours (with resolution to ≤ grade 1 or baseline).
 - Grade 3 fatigue lasting < 7 days.
 - Grade 3 laboratory abnormalities that are asymptomatic and not considered clinically significant by the Investigator, that respond to or do not require intervention and resolve to ≤ grade 1 or baseline ≤ 28 days after the last infusion of SL-401.
- Grade 4 transaminase or CPK elevation (confirmed within 24 hours of initial identification) regardless of duration or relationship to SL-401.

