7.7.2.3 Events Requiring Holding of SL-401

Withhold SL-401 infusion if any of the following occur:

- Body temperature ≥ 38°C
- HR ≥ 130 or ≤ 40 bpm
- Systolic BP ≥ 160 or ≤ 80 mmHg
- Serum creatinine > 1.8 mg/dL
- Serum albumin < 3.0 g/dL (SL-401 will be withheld for the remainder of the study cycle).
- AST > 5 × the ULN or ALT > 5 × the ULN (SL-401 will be withheld for the remainder of the study cycle).
- Increase in body weight by ≥ 1.5 kg over weight (pre-treatment) on the prior treatment day.

In situations where SL-401 administration is postponed because of deviations in vital signs, weight or laboratory values outside of the above parameters, SL-401 may be re-administered subsequently, pending normalization of the abnormalities and pending evidence of stabilization of the underlying clinical conditions resulting in these abnormalities, as detailed below. As indicated in Section 7.3.3, postponed doses may be administered within a 10-day period following the initial day of treatment within a cycle.

In the setting of temperature ≥ 38°C, SL-401 may be administered pending resolution, provided that an appropriate evaluation for infectious etiologies has been undertaken, and provided that the Investigator determines that there is minimal likelihood of uncontrolled systemic infection including sepsis; this may occur on the same day as the temperature elevation, or on subsequent days.

In the setting of delays secondary to findings consistent with capillary leak syndrome (i.e., in the setting of resolved hypotension, tachycardia, increased weight, or albumin reductions of a magnitude lower than those warranting withholding of SL-401 for the duration of a given cycle), subsequent SL-401 infusions are to be administered pending determination by the Investigator that there is no/minimal evidence of ongoing capillary leak syndrome and pending discussion with the study Medical Monitor. Any subsequent SL-401 infusions are to be administered on days subsequent to the identification of the abnormality (i.e., not the same day the abnormality was identified).

In settings in which albumin is reduced to <3.0g/dL or in which albumin is reduced by more than 1.0 g/dL below the level at the start of the cycle (i.e. from 4.3g/dL to 3.2g/dL), no subsequent SL-401 will be administered for the duration of the cycle.

In settings in which transaminases (AST/ALT) are elevated to > 5 X ULN, no subsequent SL-401 will be administered for the duration of the cycle.

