11.2 Populations for Analysis

11.2.1 Phase 1 (Evaluable for Toxicity)

Patients will be considered evaluable for toxicity if they receive any study drug. Patients will be considered evaluable for dose limiting toxicity if they receive any study drug and are followed for the full 2 cycles or experience a DLT prior to completion of 2 cycles. All patients who are not evaluable for DLT will be replaced.

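### Sections 11.2.1 and 6.2.2 define a DLT-evaluable patient differently, so one phase 1 cohort can read 0/3 (escalate) or 0/2 (incomplete)

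*Protocol*

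**What the plan says.** **Statistics section.** Section 11.2.1 treats patients as evaluable for DLT "if they receive any study drug and are followed for the full 2 cycles or experience a DLT prior to completion of 2 cycles". It then has every non-evaluable patient replaced.

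**Design section.** Section 6.2.2 sets exposure minimums for a patient without a DLT, plus 28 days of observation in each cycle. In the Run-in Cycle "a patient must receive all 5 doses within a 10 day time period". In Cycle 1 "a patient must receive at least 3 infusions of SL-401 and 16 (approximately 75%) doses of POM". The synopsis agrees with 6.2.2; for the Run-in Cycle it says "all patients must complete 5 doses of therapy".

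**Rules that end dosing.** Section 7.7.2.3 ends SL-401 for the rest of the cycle if albumin drops below 3.0 g/dL, if it falls by more than 1.0 g/dL from the start of the cycle, or if AST or ALT exceeds 5 × ULN. Its example of the albumin fall reads "i.e. from 4.3g/dL to 3.2g/dL), no subsequent SL-401 will be administered for the duration of the cycle".

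**What is not a DLT.** Section 6.2.2 exempts "Grade 3 laboratory abnormalities that are asymptomatic and not considered clinically significant by the Investigator", provided they respond to or need no intervention and resolve. Among transaminase elevations, only grade 4 is a DLT regardless of duration or relationship.

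**What happens next.** Under Section 6.2.1, "Patients who do not experience a DLT during the Run-in Cycle will have POM/DEX" added.

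**Replacement.** The synopsis refers to not completing the first cycle, and Section 6.2.1 to not completing the first 2 cycles; both add that replacement is made if needed to evaluate the cohort. Sections 5.4 and 6.2.2 name patients who leave for progression or for reasons unrelated to therapy.

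**The concern.** The 3+3 rule in Section 6.2.1 turns on counts of 0/3 and 1/6, so the definition of a countable patient is part of the escalation rule. The protocol gives two definitions, and its own safety rules can produce patients on whom they differ. Section 6.2.1 speaks of patients treated, which does not choose between them.

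The MTD, or maximum tested dose, is a primary objective and sets the phase 2 dose. Section 6.2.3 requires at least 6 evaluated patients to confirm the MTD. If patients who received only part of the Run-in dosing count as DLT-free, a dose can be cleared partly on people who never received it in full. If they do not count, it is unclear whether they are to be replaced.

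**Working it through.** **1. The protocol's own figures.** 16 of 21 pomalidomide doses is 16/21 = 76.2%, consistent with the stated 75%. Three dose levels of up to 6 patients give 18, as stated. Neither figure is in dispute.

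**2. Can a patient fall between the definitions?** Follow one phase 1 patient:

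- Albumin falls from 4.3 to 3.2 g/dL during Run-in dosing. The fall is 1.1 g/dL, above the 1.0 limit, so SL-401 stops for that cycle and 5 doses are not reached.
- The entry criterion is "Serum albumin ≥ 3.2 g/dL", so the final value would still admit a patient to the trial. A DLT is hard to argue on that value alone. An AST/ALT stop at grade 3 can likewise fall under the laboratory exemption.
- With no DLT, the patient is due to start Cycle 1, subject to two gates. Section 7.8 requires SL-401-related non-hematologic toxicity to have resolved to grade 1 or baseline. Table 13 footnote g requires Cycle 1 Day 1 chemistry to be within the entry values. Section 3.5.3 reports that in most cases these laboratory values were near baseline by 14 to 28 days after the first infusion.
- The patient passes, starts Cycle 1 and is followed for both cycles.

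| | 11.2.1 | 6.2.2 and synopsis |
|---|---|---|
| Minimum Run-in dosing | any study drug | 5 SL-401 doses |
| This patient | evaluable | not evaluable |
| Cohort with two clean patients | 0/3: escalate | 0/2: incomplete |

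In the Run-in Cycle one infusion never given is enough to separate the definitions. In Cycle 1 it takes fewer than 3 infusions or fewer than 16 pomalidomide doses.

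**3. Is this patient replaced?** Under 11.2.1, no, because the patient is evaluable. Under 6.2.2, not clearly, because the patient did not leave for progression or an unrelated reason. Under 6.2.1 and the synopsis it depends on whether a cycle with stopped dosing was completed, and the two texts count different cycles.

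**4. Frequency.** Table 5 (earlier study, Regimen B) gives all infusions received by 3 of 5, 8 of 8 and 16 of 24 patients at 7.07, 9.40 and 12.50 µg/kg/day: 27 of 37, so 10 did not. At most one of those 10 had a DLT, because the DLT patient at 9.40 was among 8 who received everything. At least 9 therefore missed infusions without a DLT. No reasons are given. Anyone who stopped for progression, death or withdrawal and was not followed for two cycles would fail both definitions. The share on whom the definitions differ is therefore unknown.

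**5. Direction.** Let *q* be the share of treated patients who count only under 11.2.1. All are DLT-free, so the DLT risk among patients counted under 11.2.1 is (1 − *q*) times the risk among those counted under 6.2.2 with replacement. The bare 3+3 escalation probability is E(p) = (1 − p)³ + 3p(1 − p)⁵, which falls as p rises. With assumed *q* of 10% and 33%, and an assumed 30% risk, E(0.30) = 0.494:

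| Meaning of the 30% | *q* | Under 11.2.1 | Under 6.2.2 |
|---|---|---|---|
| Risk at full dosing | 10% | E(0.27) = 0.557 | 0.494 |
| Risk at full dosing | 33% | E(0.20) = 0.709 | 0.494 |
| Risk per treated patient | 10% | 0.494 | E(0.333) = 0.428 |
| Risk per treated patient | 33% | 0.494 | E(0.45) = 0.234 |

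The direction is the same in every row. The size depends on *q* and on what the 30% means, and the protocol fixes neither.

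**The case against.** **The more specific rule will be used.** The Data Safety Review Committee (DSRC) may well apply 6.2.2, which is detailed and repeated in the synopsis. Section 6.2.1 also has it weigh laboratory abnormalities before each escalation, so a stopped patient should not go unseen. This lowers the practical risk, but the statistics section still gives a different definition.

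**The group is narrow.** The patient must avoid a DLT, pass the Cycle 1 gates and be followed for both cycles. Section 3.5.3 also places the albumin minimum about one week, and the liver-test peak about two weeks, after the first infusion, so much of the change comes after the usual Days 1 to 5. This narrows the group without emptying it.

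**Stronger readings that the protocol does not support.**

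- A reader might infer that the reported list of DLTs would differ by definition. It would not: a patient with a DLT is evaluable under both.
- A reader might take the Table 5 shortfall as the rate of disputed patients. It gives no reasons for missed infusions. The disease differs, Section 6.1 gives 18 rather than 24 patients at 12.5 µg/kg/day, and Section 3.5.6 describes withholding for albumin reductions as an added precaution in this study.
- A reader might add pomalidomide holds under Table 11 as a second source. Section 7.7 and the synopsis, read literally, bar dose modifications in Cycle 1 without a DLT, apart from the SL-401 holds. Table 13 footnote q concerns SL-401 administration and does not settle the matter.
- A reader might say that 5.4 and 6.2.2 forbid other replacements. They name one group without saying it is the only one, and 5.4 allows additional patients at the sponsor's discretion.

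**Conclusion.** The contradiction stands on the text and should be fixed. Sections 11.2.1 and 6.2.2 cannot both define who is DLT-evaluable, and nothing ranks them. For one identifiable type of patient the choice changes a cohort from 0/3 to 0/2, and it changes who counts toward the 6 patients in Section 6.2.3.

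Confidence is high on the mismatch and on its direction: 11.2.1 makes escalation easier by counting under-dosed patients as DLT-free. The direction rests on those patients being DLT-free by definition and on 6.2.2 being applied with replacement. No frequency is claimed, and the escalation probabilities are illustrations under assumed inputs. It also does not follow that the trial would escalate wrongly, since the DSRC could apply 6.2.2 and reviews laboratory findings.

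The replacement texts are a second, smaller inconsistency. The clearest conflict is first cycle in the synopsis against first 2 cycles in 6.2.1. The main gap is the patient made non-evaluable by a treatment-related stop.

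**What to change.** 1. In Section 11.2.1, replace the DLT-evaluable definition with the 6.2.2 criteria: a DLT in the Run-in Cycle or Cycle 1, or the stated minimum exposure and 28 days of observation in each.
2. Use one replacement rule in Sections 5.4, 6.2.1, 6.2.2 and 11.2.1 and in the synopsis: any patient without a DLT who is not DLT-evaluable over the Run-in Cycle and Cycle 1 is replaced if needed to evaluate the cohort.
3. Make sure the laboratory review that the DSRC already performs under 6.2.1 shows toxicity-related SL-401 stops in patients who are not DLT-evaluable, so that leaving them out of the denominator does not hide them.

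The cost is amendment wording, with no new assessments or visits for patients already enrolled. The drawback is time: a cohort with a stopped patient may need a replacement, who adds a Run-in Cycle and Cycle 1 (28 + 28 = 56 days). Section 11.2.1 already calls for replacing non-evaluable patients, so the principle is not new.

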11.2.2 Phase 2 (Evaluable for Toxicity)

Patients will be considered evaluable for toxicity if they receive any study drug. Patients in phase 2 will not be replaced based on toxicity.

11.2.3 Phase 1 and 2 (Evaluable for Response)

Patients will be considered evaluable for response if they have baseline disease assessments, received at least 1 cycle of therapy and have had their disease re-evaluated. These patients will have their response classified according to the IMWG response criteria. All patients in phase 2 and those treated at the recommended phase 2 dose in phase 1 who are not evaluable for response will be replaced.

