Blood will be sampled to continue to characterize the PK of SL-401 on Day 1 and 5 of the Run-in Cycle and Cycle 1. Plasma sampling will be conducted for 6 hours on each day. In Cycle 2 (infusion 1 and 5), POM and DEX (Day 1 only) will be administered 6 hours after SL-401. Plasma concentration data over time will be used to characterize the PK disposition of SL-401, to assess any change in the PK properties of SL-401 during the 5-day course of treatment or between cycles of treatment, and relate the PK characteristics of SL-401 to immunogenicity, toxicity, and disease activity. The nominal blood sampling time schedule is summarized in the Time Points for PK Blood Draw Table (Table 14).

Immunogenicity Studies:

Blood samples (serum) will be collected for the detection of SL-401 reactive antibodies. The blood sampling time schedule is summarized in the Schedule of Events (Table 13).

Statistical Considerations

Sample size determination:

The primary objectives of phase 1 of the study are to evaluate the safety of SI-401 as a single agent in an initial Run-in Cycle, to determine the MTD or the maximum tested dose where multiple DLTs are not observed and to further characterize the safety profile of SL-401/POM//DEX at the MTD. Based on such, a recommended dose for phase 2 studies will be defined. A maximum of 3 dose levels (7, 9 and $12 \mu g/kg/day$) is anticipated and thus the total number of patients for this stage ranges from 6 to 18. The anticipated sample size is sufficient to evaluate these objectives. A secondary objective is to characterize the anti-tumor activity of SL-401/POM/DEX in terms of PFS-6. During phase 2, if approximately 14 patients are enrolled at the recommended phase 2 dose as defined in phase 1 over 12 months and follow-up continues for 12 months after the last enrolled patient, the total of 20 patients treated at this dose has approximately 75% power with a 1-sided type I error rate of 5% to reject the null hypothesis that the PFS-6 is <40% if the true rate is 60%.

Analysis population:

The all-treatment population is defined as all registered patients exposed to the study drug regardless of the amount of treatment administered. Safety and efficacy will be evaluated using the all-treated population. This population will include all patients who signed informed consent and who actually received at least 1 dose or a part of a dose of SL-401 or SL-401/POM/DEX.

General statistical approach:

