5.4 Replacement of Patients

At the discretion of the Sponsor, additional patients may be enrolled to supplement patient data compromised due to premature study dropout or other reasons. During phase 1, patients who discontinue the study prior to completing the DLT evaluation period because of disease progression or for reasons unrelated to study therapy will be replaced. All patients in phase 2

and those treated at the MTD or recommended phase 2 dose as established in phase 1, who are not evaluable for response will be replaced.

6 Investigational Plan

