11.3 Determination of Sample Size

The primary objectives of phase 1 of the study are to evaluate the safety of Sl-401 as a single agent in an initial Run-in Cycle, to determine the MTD or the maximum tested dose where multiple DLTs are not observed and to further characterize the safety profile of SL-401/POM//DEX at the MTD. Based on such a recommended dose for phase 2 studies will be defined. A maximum of 3 dose levels (7, 9, and 12 μg/kg/day) is anticipated and thus the total number of patient for this stage ranges from 6 to 18. The anticipated same size is sufficient to evaluate these objectives. A secondary objective is to characterize the anti-tumor activity of SL-401/POM/DEX in terms of ORR, CBR, PFS and PFS-6. During phase 2, if approximately 14 patients are enrolled at the recommended phase 2 dose as defined in phase 1 over 12 months and follow-up continues for 12 months after the last enrolled patient, the total of 20 patients treated at this dose has approximately 75% power with a 1-sided type I error rate of 5% to reject the null hypothesis that the PFS-6 is <40% if the true rate is 60%.

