11.6 Analyses of Efficacy Data

The study will preliminary evaluate the activity of the SL-410/POM/DEX regimen. Secondary efficacy endpoints will include: PFS and PFS-6; ORR (CR + VGPR + PR) and clinical benefit rate (CR + VGPR + PR + MR) based on IMWG defined response criteria, as well as DOR; and OS. Response rates and depth of response will be calculated as the percent of evaluable patients that have confirmed sCR/CR/VGPR or PR, and exact 95% confidence intervals will be calculated for these estimates. Time to response, duration of response, and survival will be estimated using the product-limit method of Kaplan and Meier. For subgroups of patients defined by disease and line of therapy, exact 1-sided 95% confidence intervals will be calculated

for ORR and clinical benefit rates, and the distributions for duration of response, PFS, PFS6, and OS will be estimated by Kaplan-Meier methodology.

Efficacy assessment parameters will include:

- M-protein determination using both of the following procedures:
 - SPEP and serum protein immunofixation with quantitative immunoglobulins; and
 - UPEP and urine protein immunofixation (all using the same 24-hour urine collection)
- Serum FLC
- BM to quantify percent MM cell involvement
- Plasmacytoma evaluation: PET/CT scan or MRI and or physical exam as clinically indicated
- Skeletal survey
- Serum β2 microglobulin
- Cytogenetic analysis/FISH from BM aspirate

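### Section 11.6 computes response rates on evaluable patients while the synopsis and 11.1 use all treated patients, and the replacement rule takes early failures out of the response denominator

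*Protocol*

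**What the plan says.** **Population.** The synopsis, under analysis population, states: "Safety and efficacy will be evaluated using the all-treated population". Protocol 11.1 likewise bases analyses on everyone who received any amount of study treatment. Protocol 11.6, however, has response rates "calculated as the percent of evaluable patients that have confirmed sCR/CR/VGPR or PR".

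**Who is evaluable.** Protocol 11.2.3 asks for baseline disease assessments, at least one cycle of therapy and a disease re-evaluation.

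**Replacement.** Protocol 5.4 and 11.2.3 replace all phase 2 patients who fail that definition, and also "those treated at the recommended phase 2 dose in phase 1 who are not evaluable for response will be replaced". Protocol 11.2.2 says: "Patients in phase 2 will not be replaced based on toxicity". A separate phase 1 rule in 5.4 replaces "patients who discontinue the study prior to completing the DLT evaluation period because of disease progression or for reasons unrelated to study therapy".

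**PFS-6.** Protocol 11.3 rests its power statement on "the total of 20 patients treated at this dose". The power claimed, at 40% against 60% PFS-6, is "approximately 75% power with a 1-sided type I error rate of 5"%. Protocol 11.6 names Kaplan-Meier for PFS and PFS-6 and sets no evaluable-only restriction.

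**The concern.** The two denominators cannot both apply to ORR. The difference between them depends on outcome: the patients who fall out of the evaluable set are those whose first cycle ended early through death, clinical progression or toxicity. Few of them can be responders, so the evaluable rate errs in one direction. Replacement then refills the 20 places with patients who got past that point. An analysis plan written later can choose a denominator, but it cannot settle what sites should do under two replacement rules during enrolment.

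ORR, clinical benefit rate and PFS-6 are the trial's evidence of activity. They come from a single open-label arm of about 20 patients at the phase 2 dose, where one patient is 5 percentage points.

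**Working it through.** **1. The rules applied to one patient.** Take a phase 2 patient whose toxicity ends cycle 1 before any re-evaluation.
- Synopsis and 11.1: in the efficacy analysis.
- 11.2.3 with 11.6: not evaluable, outside the ORR denominator.
- 5.4 and 11.2.3: replaced.
- 11.2.2: not replaced, if the ground is taken to be toxicity.

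These give opposite answers on the denominator and, for this patient, on replacement.

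**2. Size for ORR.** Let q be the share of treated patients who are excluded, with no responders among them. Then reported ORR = true ORR / (1 − q). The protocol gives neither a target ORR nor q. As illustration I use the 33% that section 3.5.5 cites for pomalidomide plus dexamethasone, and I assume q.

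| q (assumed) | Reported ORR | Excess, points |
|---|---|---|
| 5% | 0.33/0.95 = 34.7% | 1.7 |
| 10% | 0.33/0.90 = 36.7% | 3.7 |
| 13.1% | 0.33/0.869 = 38.0% | 5.0 |

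The 13.1% comes from the protocol's own null. Constant hazard with PFS-6 of 40% is −ln(0.40)/6 = 0.1527 per month. One 28-day cycle is 28/30.44 = 0.92 month, and 1 − exp(−0.1527 × 0.92) = 13.1%. It is about the upper bound for progression or death in the first cycle under that null. Toxicity stops without progression would come on top.

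For scale, the standard error of a 33% rate in 20 patients is √(0.33 × 0.67/20) = 10.5 points.

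**3. Reproducing the stated power for PFS-6.** Inputs from 11.3: n = 20, one-sided 5%, 40% against 60%, 12 months of accrual and 12 months of further follow-up.
- Hazards: 0.1527 (null) and −ln(0.60)/6 = 0.0851 (alternative) per month; ratio 0.557.
- Event probability under the alternative, uniform accrual: 1 − (e^(−0.0851×12) − e^(−0.0851×24))/(0.0851 × 12) = 0.774, so 20 × 0.774 = 15.5 events.
- Power = Φ(√15.5 × |ln 0.557| − 1.645) = 74.4%. Simulation gives 75.2%.

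A one-sample exponential test therefore reproduces the stated 75%.

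**4. PFS-6 if replaced patients were dropped.** The same test was simulated 200,000 times under the null, with a given share of first-cycle events replaced and left out.

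| Share of first-cycle events replaced | Apparent PFS-6 | Type I error |
|---|---|---|
| None | 40.0% | 3.6% |
| A quarter | 41.3% | 4.6% |
| Half | 42.8% | 6.0% |
| All | 46.0% | 10.4% |

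The nominal 5% is exceeded at half and above, but not at a quarter.

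**5. If replaced patients stay in.** PFS-6 under the null remains 40%. The number treated to obtain 20 evaluable patients is 20/(1 − q), or 21.1, 22.2 and 23.0 at q = 5%, 10% and 13.1%.

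**The case against.** The best defence is that evaluability for response governs response classification and nothing else. PFS and PFS-6 are Kaplan-Meier estimates, the general rule is all treated, and no section removes a replaced patient from them. This stands: inflation of PFS-6 is a possibility that 11.3 leaves open, not something the protocol prescribes.

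Several stronger readings are tempting and are not supported:
- That ORR is inflated against a fixed null. The 40% null belongs to PFS-6. ORR has no null or target, so it has no false-positive rate.
- That the error rate can be read from a cut-off of 12 or 13 successes in 20. The protocol states no such rule, and exact power at 60% would be 59.6% or 41.6%, not 75%.
- That every phase 1 failure during the two-cycle DLT period is lost. That replacement rule concerns DLT evaluability. Section 6.2.1 assesses response after the Run-in Cycle, so a patient who completes it, is re-evaluated and then progresses is response-evaluable and counts.
- That the sponsor's discretion in 5.4 adds to the bias. It allows patients to be added and removes none.

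The first-cycle share is also a generous bound. Progression found at the scheduled assessment after a completed cycle leaves the patient evaluable. The evaluable sentence in 11.6 does not list minimal response, so the same denominator for clinical benefit rate is an inference. Finally, 11.2.2 and 11.2.3 name different grounds for replacement and collide only for toxicity that ends cycle 1.

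None of this removes the conflict over the ORR denominator.

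**Conclusion.** The protocol fixes two conflicting efficacy populations. If 11.6 is followed, ORR is biased upward, and clinical benefit rate too if it uses the same denominator. On the illustrative 33%, the excess is 1.7 to 5.0 points for 5% to 13% excluded, assuming no responders among them. That is smaller than the sampling error of 20 patients, but it always runs in the favourable direction and is avoidable.

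For PFS-6 the bias arises only if replaced patients leave the set. The synopsis and 11.1 imply that they stay, while 11.3 counts 20 without settling it. The resulting type I error of 4.6% to 10.4%, against 3.6%, assumes constant hazard and the exponential test, which is inferred from the stated power and not named in the protocol.

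The wording should be corrected. It does not threaten the primary objectives, which are safety and the maximum tolerated dose; efficacy is secondary and described as preliminary.

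**What to change.** - **11.2.3 and 11.6:** make the denominator for ORR and clinical benefit rate all patients treated at the phase 2 dose. Retain replaced patients, and count those without a post-baseline assessment as non-responders. Report evaluable-patient rates as supportive only.
- **11.3 and 11.6:** state that PFS and PFS-6 include all treated patients from first dose, so that replacements add to the 20 and do not substitute for earlier patients.
- **5.4, 11.2.2 and 11.2.3:** state one replacement rule for phase 2 patients whose toxicity ends cycle 1.

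The cost is wording and slightly less favourable reported rates. Little new data collection is needed, because 6.4 and 7.9.2 already follow patients who stop for reasons other than progression every month until progression or subsequent therapy.
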